Trial Protocol

Project Title: Effectiveness of e-based cognitive behavioral therapy for insomnia on improving mental health in Chinese youths with insomnia: a large-scale randomized control trial

Introduction

Depression in Youth

Youth is a sensitive and critical period of development marked by considerable changes in biological, cognitive, psychological and social functioning. It is also a vulnerable transitional stage often linked to the emergence of mental health problems. In particular, major depressive disorder (MDD) is among the most common psychiatric disorders in the youth population, and has become the leading cause of disability adjusted life-years (DALYs) for females aged 20-24 year.¹ Two large epidemiological surveys reported that depressive symptoms were present in 13.8%- 21.0% of college students, and a recent meta-analysis showed that the prevalence estimate of depression or depressive symptoms among medical students is 27.2%.²⁻⁴ Youth depression is associated with substantial psychosocial and functional impairments (e.g. poor school achievement, impaired social skills, interpersonal difficulties, substance abuse) and an elevated risk of suicidal behaviour and completed suicide.^{5, 6} In addition, youth depression has been found to predict recurrent depression in adulthood and be associated with long-term functional impairment.^{7,8} Although the treatments for youth depression, such as cognitivebehavioral therapy and interpersonal approaches, have been widely investigated with substantial progress, non-response to treatment, residual symptoms and relapses/recurrence were commonly reported (e.g. up to 50% of the treated adolescent cases experienced a recurrence).⁹ Moreover, young people are often reluctant to initiate help seeking face-to-face for mental health problems, because of the fear of stigma and a preference of self-reliance.¹⁰ Thus, youth depression is often left untreated. According to national surveys conducted in America, only 24% of college students with depression were under appropriate treatment.¹¹ In view of its high prevalence, persistence, deleterious long-term impacts and treatment challenges, there is an imperative need to develop and implement an effective prevention programme for depression, especially during early developmental stage, from a public health perspective.

Insomnia as a Target for Prevention of Depression – Rationale, Empirical Basis & Research Gaps

Interplay between insomnia and depression

Targeting insomnia may become a promising intervention to prevent depression among youth, as Insomnia and depression are highly comorbid conditions, with increasing evidence suggesting their intricate, bidirectional relationship. In particular, insomnia and depression often co-occur, with 35-47% of individuals with insomnia having clinically significant depression and 60-84% of people with MDD experiencing comorbid insomnia symptoms.¹² Rather than a symptom of depression, insomnia is an independent problem which commonly precedes the development of depression,¹³ and has been found to increase the risk of developing incident new depression,^{14, 15} lead to poorer treatment response,¹⁶ increase the susceptibility of having recurrence,¹⁷ and represent an independent risk factor for suicidal ideation and behaviour.¹⁸⁻²⁰ This growing body of

evidence emphasise the unique, independent role of insomnia in the course of MDD, and interventions which directly target insomnia are most likely to improve depression outcomes, or may even prevent depression.

The mechanisms underlying the comorbidity of depression and insomnia have provided clues for further validating the preventive effect of insomnia treatments on depression. In biological domain, the most widely adopted theory is hyperarousal theory.^{21, 22} Evidence has clearly shown that stress-activated hypothalamic-pituitary-adrenal (HPA) axis hyperactivity exists in both depressed and insomniac patients. ²³⁻²⁵ Moreover, arousal responses of HPA axis is associated with slow wave sleep deficit and sleep continuity disruption in both depression and insomnia.²⁶⁻²⁸ In psychological domain, maladaptive cognitions and behaviors, such as worry, ruminations, vulnerability to stress and poor problem solving skills, are implicated in the association between depression and insomnia.^{22, 29} Additionally, a temporal relationship between depression and insomnia also favours the idea that effective treatment of insomnia would lower the risk of depression. As mentioned above, the occurrence of insomnia commonly precedes depression in most cases, and several longitudinal studies have demonstrated that previous insomnia was related to subsequent onset of depression.³⁰⁻³³ A meta-analytic review revealed that insomniac patients without depression at baseline have a twofold risk to develop depression.¹⁵ These evidences further indicated that insomnia could play a causal role in the onset of depression.²⁶

Cognitive behavioral therapy for insomnia

Cognitive behavioral therapy for insomnia (CBT-I) is a multi-component, nonpharmacologic intervention that targets behavioral, cognitive and physiological perpetuating factors of insomnia. There is a strong evidence base to support the shortterm and long-term efficacy of CBT-I for chronic primary insomnia in adults.^{34, 35} A metaanalysis has validated the comparable treatment efficacy between CBT-I and pharmacotherapy during short-term treatment.³⁶ and CBT-I is more effective than pharmacotherapy in long-term treatment.³⁷ Additionally, CBT-I can benefit youth other than adults. A recent systematic review showed that CBT-I had large effects on various sleep variables and medium effects on mental health among college students, whereas other psychological interventions such as sleep hygiene and relaxation showed small to medium effects for sleep variables.³⁸ Moreover, the preliminary results from our ongoing research showed that CBT-I significantly improved insomnia symptoms in adolescent patients with insomnia (Trial registration: clinicaltrials.gov Identifier: NCT03522701) and could prevent incident acute insomnia in the high-risk adolescents who genetically predisposed to insomnia and presented with subclinical insomnia symptoms (Funded by General Research Fund, Ref. CUHK 4012-PPR-11).

Apart from its direct effects on sleep improvements, CBT-I can also be effective in reducing depressive severity. In line with the findings in previous studies [36, 61-63], our research team has validated the effectiveness of CBT-I for improving both depressive and insomnia symptoms in patients suffering insomnia and depression (Funded by Health and Medical Research Fund, Ref. 10110341). In a randomized trial which compared treatment effects of CBT-I and CBT for depression (CBT-D) in patients with comorbid MDD and insomnia, CBT-I was more effective than CBT-D in reducing insomnia

severity, and equally effective in reducing depressive severity [64], indicating the importance of applying insomnia treatment for patients with both insomnia and depression.

Digital approach to treatment of insomnia for preventing depression in youth

While face-to-face CBT-I has shown promise in management of insomnia and psychiatric conditions such as depression, several barriers to implementation remain in clinical practice. Firstly, face-to-face CBT-I appears to be time-consuming for therapists in practice.³⁹ Moreover, there are not enough therapists qualify for offering CBT-I.^{40, 41} Thus, it is important to develop alternative delivery modalities of CBT-I which have comparable efficacy of standard face-to-face CBT-I and can improve its feasibility. Two major variants of CBT-I that may address barriers impacting CBT delivery are internetdelivered CBT-I (e-CBT-I) and group CBT-I. A recent meta-analysis revealed that e-CBT-I and face-to-face CBT-I had comparable effects on insomnia and other sleep-related symptoms,⁴² and meta-analysis of group CBT-I showed that group CBT-I is also an effective treatment for insomnia, as it has large effect sizes for sleep onset latency, sleep efficiency, and wake after sleep onset.⁴³ As for youth with insomnia, a series of studies conducted by a research team in University of Amsterdam showed that both e-CBT-I and group CBT-I were well accepted and highly feasible with low dropout rates.^{44, 45} Further, two treatment modalities were effective for youth with insomnia and no significant differences were found between these two formats. However, this research team found that e-CBT-I was more cost effective than group CBT-I in treating youth insomnia.⁴⁶ Moreover, internet has the capacity to reach a large group of young people given their increased accessibility and frequent use of web and smartphone technology,^{47, 48} and is important in their daily lives.⁴⁹ Therefore, e-CBT-I may be a preferable alternative for youth with insomnia.

Currently, researchers have done considerable work to investigate whether e-CBT-I could be effective in improving psychological well-being for adults. To our knowledge, to date there is two randomised controlled trial (RCT) to particularly test whether indicated preventive intervention for insomnia could prevent depression in adults.^{50, 51} Christensen et al. and Cheng et al. both showed promising results of e-CBT-I in alleviating depressive symptoms in their study, and the effects persisted at 1-year follow-up and 18-month follow-up, respectively. However, Christensen et al. found that emergence of MDD was low in targeted sample and did not conduct clinical assessment at 18-month follow-up. By using self-report scale instead of clinical assessment, Cheng et al. found that in those with minimal to no depression at baseline, the incidence of moderate to severe depression at 1-year follow-up in the dCBT-I condition was less than half that in the control condition. Another study further demonstrated that the effects of e-CBT-I on improving psychological health were mediated by a reduction of insomnia symptoms.⁵²

Despite these findings, there are some issues of current studies that need to be addressed in the future. As the existing data on e-CBT-I mostly came from the studies based on the adult samples, little is known as to whether timely intervention of sleep disturbance could potentially serve as a preventive measure to alter the trajectory of youth depression. Nevertheless, previous studies showed that improving sleep via e-CBT-I in college students leaded to a reduction in psychotic symptoms such as hallucinations and paranoia,⁵³ and e-CBT-I could also alleviate anxiety severity in college students with insomnia.⁵⁴ Therefore, further research is warranted to evaluate the effects of e-CBT-I on reducing depressive symptoms in youth. Another issue is that it is still unclear by which mechanisms e-CBT-I might affect mental health. The improvement of mental health achieved with e-CBT-I might simply attribute to the reduction of insomnia symptoms as indicated in previous study,⁵² or it might due to reverse the effects of poor sleep hygiene, sleep-related unhelpful thoughts and maladaptive behaviors, circadian rhythm disruption and chronic sleep deprivation.⁵⁴ Additionally, previous studies mainly focused on evaluating the changes of psychological outcomes, and only one study showed that e-CBT-I could lower the risk of depression. In this study, depression was assessed by self-report scale instead of clinical assessment. Thus, the findings should be replicated and assessments that are more reliable should be adopted in other independent studies.

To address the limitations in the existing literature, we propose to conduct a RCT of targeted prevention intervention to validate the treatment effect of e-CBT-I on insomnia disorder and examine whether digitally delivered insomnia treatment can reduce the risk of depression in a high-risk group of youth population. To further explore the mechanisms underlying the association between insomnia treatment and depression, we will evaluate whether changes in candidate factors including insomnia symptoms, mood symptoms, sleep-related unhelpful thoughts and maladaptive behaviours, and circadian rhythm disruption will mediate the changes in depressive symptoms. On a conceptual level, the proposed interventional study will also allow us to further test the causal pathway between sleep disturbance and major depression, by intervening and treating insomnia as a preventive measure of depression. On a pragmatic level, digital approach to insomnia intervention for prevention of youth depression, if effective, may have important public health implications given its high accessibility to the young populations.

Methodology

Study Design

A randomized, assessor-blind, parallel group-controlled trial will be conducted in youth with insomnia and subclinical depression. All qualified participants will be randomly assigned via online system to receive e-CBT-I or health education (HE). Randomization will be stratified by sex and the severity of insomnia. Assessments will be carried out at baseline, post-treatment, 6-month follow-up and 12-month follow-up. Additional assessments will be given upon the completion of sessions 2 (post-session 2) and 4 (post-session 4) to evaluate sleep symptoms, mood symptoms, circadian rhythms and sleep parameters of participants. Saliva collection kit will be mailed to participants at baseline to collect their salivary cortisol and DNA, and at 12-month follow-up to collect their salivary DNA. Semi-structural individual interviews about user experience and satisfaction towards e-CBT-I intervention via phone calls will be given to part of the participants in e-CBT-I group after intervention.

Main hypothesis in the present study include:

1. Youth receiving e-CBT-I will have fewer onsets of depressive disorder and higher rates of remission in insomnia disorder at post-intervention, 6-month and 12-month compared

to those in control group.

Youth in e-CBT-I group will have fewer insomnia symptoms, depressive symptoms, suicidal ideation, plans and attempts than those in control group at each timepoint.
 Changes in candidate factors including insomnia symptoms, mood symptoms, circadian rhythms and sleep parameters will mediate the outcomes.

Recruitment and Screening

Potential participants will be recruited from colleges and senior secondary school in Hong Kong and mainland China and will be identified from various sources. These will include the local partner schools in Hong Kong established from our previous research projects. Partner schools in mainland China will be recruited by our collaborators with the school links in mainland China. Through our partner schools, students will be introduced to this study, and they will be asked to return the signed informed consents and leave their contact (e.g., email) in the reply slip to the research team if they are interested in taking part in the study. Furthermore, potential participants will be recruited through community referrals and advertising via social media and emails in Hong Kong and mainland China. Interested participants will be asked to complete the screening assessments, including Patient Health Questionnaire-9 (PHQ-9)⁵⁵ and Insomnia Severity Index (ISI)⁵⁶ via an online portal (Qualtrics). Participants who have an ISI score of no less than 15 and a PHQ-9 score between 4 and 20 will be further invited for diagnostic interview through telephone to screen for insomnia (International Statistical Classification of Diseases and Related Health Problems10th Revision Classification of Mental and Behavioral Disorders, ICD-10 Classification of Mental and Behavioral Disorders ⁵⁷), MDD and suicidality including ideation, plans and attempts (Mini International Neuropsychiatric Interview, MINI ⁵⁸). A potential participant who meets the inclusion criteria (see below) will be eligible to take part in the study.

Participants

Inclusion criteria and exclusion criteria for participants are as follows:

Inclusion criteria

- 1. Native Han youth in Hong Kong and mainland China, aged between15-25
- 2. A diagnosis of insomnia disorder measured by ICD-10 Classification of Mental and Behavioral Disorders
- 3. The presence of moderate or severe insomnia measured by a score of 15 or above on ISI
- 4. The presence of subclinical depression assessed by a score of more than 4 but less than 20 on PHQ-9
- 5. Access to smartphones
- 6. Ability to read and understand research protocol

Exclusion criteria

- 1. Shift workers
- 2. The presence of prominent suicidality (suicide plans and suicide attempts) measured by MINI via telephone interview
- 3. A clinical diagnosis of psychosis, schizophrenia, bipolar disorder, or neurodevelopmental disorders

- 4. Current medical conditions that could cause poor sleep quality and sleep continuity disruption, such as eczema
- 5. The presence of current MDD or a prior episode of MDD within past two months measured by MINI via telephone interview
- 6. Women during pregnancy or lactation
- 7. Currently receiving psychological treatment for insomnia provided by a psychologist and/or pharmacological treatment for depression

Intervention

The e-CBT-I will be delivered by a mobile application (eSleep) which contains a digital, self-paced, and highly interactive programme. The Chinese version (simplified Chinese/Mandarin) of the application has been designed to adapt for the language background of the participants in China. The program is developed as based on wellestablished CBT-I treatment protocol and consists of six 20-30 minutes sequential modules unlocked weekly with animated elements, including an overview of sleep, sleep restriction, stimulus control, cognitive therapy, structured worry time and relapse prevention. During sleep restriction module (session 2), participants will obtain a "sleep prescription" from the application, specifying their sleep window (from initial bedtime to final arising time) for the next seven days. The setting of the sleep window is based on individual's average total sleep time from the previous week, while adhering to the 5hour minimum rule. The sleep prescription is adjusted weekly based on the following criteria: 1) if sleep efficiency > 85%, increase sleep window by 15-20 min; 2) if sleep efficiency < 80%, decrease sleep window by 15-20 min; and 3) if sleep efficiency is between 80%-85%, keep sleep window the same. The application control management system provides online analytics, which allows the researchers to monitor individual's participation during the intervention by assessing how many sessions were completed and the number of weeks to complete the course. Participants will have access to the e-CBT-I treatment for 12 weeks, allowing them additional time to complete the intervention in case they were unable to completed it within the initial 6-week period. Individualized text messages will be sent to the participants regularly, asking them to complete the treatment sessions and sleep diaries on time. The participants will also be contacted weekly to prevent possible dropout from occurring during the intervention. The PI and collaborators have had the research and clinical experiences in delivering CBT-I, and the e-CBT-I treatment protocol has been tested and modified from our previous studies [Trial registration: clinicaltrials.gov Identifier: NCT03438331; funded by Early Career Scheme, Ref. 27613017] 59.

The HE, a psychoeducation/information-approach, delivered in control group has been adopted in the previous study ⁵⁰. It also consists of six consecutive sessions which contains information about general sleep knowledge, functions of human organs, nutrition, environmental health, brain health, identification and treatments of common diseases, but the contents are not related to any active therapeutic components of CBT-I. Each module was unlocked weekly, and participants will have access to the intervention for 12 weeks. The general sleep knowledge session was purposively added in this sleep related RCT to meet the expectation of the participants. Individualized text messages will be sent to the participants regularly to remind them of completing the sessions and sleep diaries on time. The participants will also be contacted weekly to prevent possible dropout from occurring during the intervention.

Assessments

Assessments will be delivered at baseline, post-treatment, 6-month follow-up and 12month follow-up. At baseline, all participants will be interviewed for their basic demographic and clinical characteristics (age, sex, education, height, weight, current medications etc). Self-administered questionnaires will be completed online to assess depressive symptoms and severity (PHQ-9), anxiety (Generalised Anxiety Disorder 7item, GAD-7⁶⁰), suicidal ideation (Beck Scale for Suicide Ideation, BSSI⁶¹), sleep symptoms (ISI, 7-Day Daily Sleep Diary), daytime symptoms (Multidimensional Fatigue Inventory, MFI⁶²), chronotype (reduced Morningness-Eveningness Questionnaire, rMEQ ⁶³), sleep-related thoughts and behaviors (brief version of dysfunctional beliefs and attitudes about sleep, DBAS-16⁶⁴), circadian rhythms and sleep parameters (7-Day Daily Sleep Diary). During the intervention, participants will additionally complete ongoing assessments to evaluate their sleep symptoms, mood symptoms and sleep parameters (ISI, PHQ-9, GAD-7, 7-Day Daily Sleep Diary) at post-session 2 and post-session 4. Saliva collection kit will be mailed to participants at baseline to collect their salivary cortisol and DNA, and at 12-month follow-up to collect their salivary DNA. After finishing the intervention, each participant will be paid CNY100 (or HKD equivalent) for his or her participation. Part of the participants in e-CBT-I group will be invited to receive semi-structural individual interviews about user experience and satisfaction towards e-CBT-I intervention via phone after intervention, and will be additionally paid CNY100 (or HKD equivalent) for his or her participation.

At post-treatment, 6-month follow-up and 12-month follow-up, participants will receive phone calls from the independent researcher blinded to the randomization status for diagnostic interviews to examine whether they have current insomnia measured by ICD-10 Classification of Mental and Behavioral Disorders, MDD or suicidality measured by MINI. Part of the diagnostic interviews will be audiotaped and second-rated by an independent rater to assess interrater reliability after obtaining participants' consents. In addition, participants will complete online questionnaires similar to those at baseline. After finishing the 12-month follow-up, each participant will be paid CNY50 (or HKD equivalent) for his or her participation.

Outcomes

The primary outcomes include remission rate of insomnia disorder conformed by ICD-10 Classification of Mental and Behavioral Disorders, change of insomnia symptoms measured by ISI, occurrence of MDD conformed by MINI and change of depressive symptoms measured by PHQ-9. Secondary outcomes include incidence of suicidality which includes plans and attempts as measured by MINI and change of anxiety symptoms measured by GAD-7. Other pre-specified outcome include incidence of suicidal ideation measured by BSSI, change of daytime symptoms measured by MFI, change of sleep-related thoughts and behaviors measured by DBAS-16, change of circadian rhythms measured by 7-Day Daily Sleep Diary and MEQ, and change of sleep parameters including time in bed (TIB), total sleep time (TST), sleep onset latency (SOL), wake after sleep onset (WASO), sleep efficiency (SE) measured by 7-Day Daily Sleep Diary.

Sample Size Estimation

The sample size calculation was based on the occurrence of diagnosed depressive disorder because the primary aim of the current study was to prevent clinical depression. According to the previous meta-analysis, the incidence rate of depression is approximately 11% in the individuals with insomnia ¹⁵. As the study sample included a mixture of individuals without prior depression and those with a history of MDD, an expected 50% increase in the cumulative one-year occurrence of diagnosed depressive disorder is anticipated (16.5%). Based on the previous research on CBT-I and our trial data on sleep-focused treatment for depression, a 50% reduction of occurrence rate is expected for the intervention group. Power analysis using Stata suggested that a total of 282 participants per condition would be required to achieve a power of 0.80 whilst allowing a type I error of 0.05 detect a hazard ratio of 0.5 under 1:1 randomization. In view of the attrition rate from previous study (40%), a total of 940 participants would be required (470 participants in each group x 2 groups). A protocol amendment was submitted to reduce the sample size to 708 (354 per group) based on an estimated attrition rate of approximately 20%, as it was determined that the attrition rate was lower than initially expected.

Data Analysis

All main analyses will be based on the intent-to-treat (ITT) approach. We aim to obtain full follow-up data on every participant, but missing data may be inevitably expected due to withdrawal, loss-to-follow-up, or non-response questionnaire items. Baseline characteristics will be presented as percentage for categorical variables and as means (standard deviations) for continuous variables. The primary and secondary outcomes with continuous variables will be examined by using linear mixed-effects model (LMM) analysis. The changes of efficacy indicators (e.g., PHQ-9) from baseline to each follow-up time points and intervention differences were tested by the MIXED module of Stata, with major measures at each time point nested within each participant. Interaction effects of group by time will be examined to compare the effects of treatment on the major outcomes. Between-group difference in the estimated mean change from baseline to each time points from mixed models and Cohen's d will be used to calculate effect sizes. Current MDD will be analyzed by the survival analysis and the Mentel-Cog log rank test. An observation will be right censored to the day after the last point of interview when a participant is no longer eligible to experience a depressive episode, e.g., lost to follow-up or completed the trial without experiencing a depressive episode (12month follow-up after intervention). The effect of the intervention on insomnia remission will be analyzed using generalized estimating equations (GEE). The GEE analysis will be conducted by using the XTGEE module of Stata. Mediation analysis using maximum likelihood estimation within a structural equation modeling framework will be used to determine which outcomes are mediated by changes in candidate factors including sleep symptoms, mood symptoms, sleep-related unhelpful thoughts and maladaptive behaviors, circadian rhythm disruption and sleep parameters at follow-up. Sensitivity analyses will be conducted using imputation methods to examine the robustness of the results based on

different assumptions about the missing data. Strata variables (sex and insomnia severity) at baseline will be included as covariates in all analyses. Variables with a p value ≤ 0.05 will be considered statistically significant.

Ethics & Other Considerations

All participants will provide their online informed consent before participation. Potential adverse effects will be evaluated by self-reporting of existing adverse effects for frequency and severity ⁶⁵. Participants will be excluded from the study and provided with information for further treatment if they are diagnosed with MDD or show a suicidal risk upon assessments. The proposed study will be conducted in compliance with the protocol, the ICH-CGP Guideline, and all other applicable regulatory requirements. The ICH shall include the elements required by the International Conference on Harmonization (ICH) Good Clinical Practice (GCP) Guideline and local regulation requirements, and will adhere to the ethical principles based on the Declaration of Helsinki.

References:

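### Four unranked primary outcomes are each judged at p ≤ 0.05 with no testing order, alpha split or success rule, so the plan does not define a positive trial

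*Combined protocol and SAP*

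**What the plan says.** - **Outcomes.** "The primary outcomes include remission rate of insomnia disorder conformed by ICD-10 Classification of Mental and Behavioral Disorders", followed in the same sentence by "change of insomnia symptoms measured by ISI, occurrence of MDD conformed by MINI and change of depressive symptoms measured by PHQ-9". That makes four primary outcomes, two on insomnia and two on depression, with no ranking.
- **Data Analysis, threshold.** The only decision rule is "Variables with a p value ≤ 0.05 will be considered statistically significant".
- **Sample Size Estimation.** The calculation is "based on the occurrence of diagnosed depressive disorder because the primary aim of the current study was to prevent clinical depression". It assumes a control one-year occurrence of 16.5% and a hazard ratio of 0.5, and gives 282 per arm "to achieve a power of 0.80 whilst allowing a type I error of 0.05", before attrition.
- **Data Analysis, MDD.** "Current MDD will be analyzed by the survival analysis and the Mentel-Cog log rank test". Participants who finish without an episode are censored at the 12-month follow-up, so MDD has one comparison over the whole period.
- **Data Analysis, the other three.** ISI and PHQ-9 go into mixed models. The text can be read as testing change to every follow-up visit, or as one group-by-time interaction test per outcome with visit differences used only for effect sizes. Remission goes into a GEE, with no primary contrast or visit named. The Study Design hypotheses place these outcomes at several visits.
- **Aims.** The last paragraph of the Introduction sets an insomnia aim beside the depression aim.

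No section gives a testing order, an alpha split, or a statement that one, some or all of the four must succeed.

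**The concern.** A confirmatory plan has to say which result makes the trial positive. Here MDD has an implied priority, because the trial is sized on it and preventing depression is called the primary aim. Nothing says that MDD decides the trial, however. A null MDD result with a significant ISI, remission or PHQ-9 result could be presented as success on a primary outcome, and the plan could not contradict it. Under that reading the trial-level type I error is above the 0.05 used in the sizing. The missing time points and contrasts for remission, ISI and PHQ-9 leave a further choice that could be made after the data are seen.

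Sizing a trial on one of several primary outcomes is not itself an error. The fault is the missing rule that connects them.

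**Working it through.** **1. Does the sizing leave any alpha for the other three outcomes?** Inputs from Sample Size Estimation: control risk 16.5%, HR 0.5, alpha 0.05, power 0.80, 1:1 allocation.

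- Freedman log-rank events: (1.960 + 0.842)² × ((1 + 0.5)/(1 − 0.5))² = 7.849 × 9 = 70.6.
- Intervention risk under proportional hazards: 1 − 0.835^0.5 = 8.6%. Mean risk: 12.56%.
- Per arm: 70.6 / 0.1256 / 2 = 281.2, rounded up to 282. This is the stated figure.

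The plan does not say whether alpha is one- or two-sided. Two-sided 0.05 reproduces 282; one-sided 0.05 gives 223 or fewer under proportional hazards. The full two-sided 0.05 is therefore spent on MDD.

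**2. Family-wise error if any one of the four counts.** Assume one two-sided 0.05 test per outcome. The documents give no correlations between test statistics, so these are assumed. For independent tests the error is 1 − 0.95^k. For a common correlation r it is 1 − ∫ φ(x) [Φ((c − √r·x)/√(1−r)) − Φ((−c − √r·x)/√(1−r))]^k dx, with c = 1.96.

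| Assumed r | All four null (k = 4) | Only MDD and PHQ-9 null (k = 2) |
|---|---|---|
| 0 | 18.5% | 9.75% |
| 0.3 | 17.4% | 9.5% |
| 0.5 | 15.6% | 9.1% |
| 0.7 | 13.0% | 8.35% |
| 0.9 | 9.4% | 7.0% |

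With two related pairs (0.7 to 0.8 within the insomnia and depression pairs, 0.3 to 0.5 between them), simulation under the global null gives 13.7% to 15.5%. For k = 2 the Bonferroni bound is 2 × 0.05 = 10% at any correlation. The k = 2 column applies if the insomnia effects are real, which the Introduction treats as likely.

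If all four had to succeed there would be no inflation. Visit-by-visit testing would raise both columns and could pass the 10% bound. The text does not clearly require it, so no figure is given.

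**3. MDD power at 282 per arm.** Power = Φ(√events × (1 − HR)/(1 + HR) − c).

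| HR | Alpha | Expected events | Power |
|---|---|---|---|
| 0.5 (plan) | 0.05 | 70.8 | 80.1% |
| 0.6 (assumed) | 0.05 | 75.4 | 58.4% |
| 0.7 (assumed) | 0.05 | 80.0 | 35.1% |
| 0.5 (plan) | 0.025 | 70.8 | 71.4% |

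**4. Splitting alpha between the two aims, with recycling.** Suppose the insomnia aim succeeds at 0.025 with probability P and its alpha then passes to MDD. For independent tests, MDD power = 0.714 + (0.801 − 0.714) × P. This gives 78.4% at P = 0.80, 79.2% at 0.90 and 79.7% at 0.95. With r = 0.5 between the MDD and insomnia tests it is 77.7% at P = 0.80 and 79.6% at P = 0.95. These values of P are assumptions.

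**5. Do the proposed rules control the error?** With MDD tested first: if MDD is null, any false claim requires a false MDD rejection, which has probability 0.05. If MDD is real, Holm holds the other three at 0.05. The two-aim split starts from 0.025 + 0.025 = 0.05 and passes alpha on only after success. Simulation of the split gave at most 0.049.

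**The case against.** **MDD is plainly the lead.** The plan calls preventing depression its primary aim and sizes only on MDD. If MDD alone decides the trial, giving it the full 0.05 is correct and there is no inflation. That is fair as a reading. But the sentence justifies the sample size and is not a decision rule. The Outcomes section lists MDD third of four, and the Introduction states the insomnia aim first. If this reading is intended, one sentence would settle it.

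**Two aims, each supporting its own claim, need no joint correction.** This can be argued, but each aim still has two primary outcomes at 0.05. The depression aim alone carries up to 9.75% with one test each.

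**The error rates are two-sided, and no one would report a result favouring health education as success.** True. Counting only false results in favour of e-CBT-I, the global-null range is 1 − 0.975⁴ = 9.6% at r = 0 to 6.5% at r = 0.7, against a nominal 2.5%. For MDD and PHQ-9 alone it is 1 − 0.975² = 4.9% at r = 0. The two-sided figures match the convention of the sizing, and the relative inflation remains.

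**The larger range needs the global null.** This also stands. The plan itself expects insomnia to improve, so the figure of at most 10% is the more realistic one, subject to one test per outcome.

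These points qualify the size of the inflation. They do not supply the missing rule.

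**Conclusion.** The concern holds and must be fixed. The omission is certain: four unranked primary outcomes, one blanket threshold, and no order, split or success rule anywhere in the combined protocol and SAP. The size is conditional. With any one success counting and one two-sided test per outcome, the family-wise error is about 13% to 19% under the global null for assumed correlations of 0.7 down to 0 (9.4% at 0.9). It is at most about 10% if both insomnia effects are real. It is not inflated if MDD alone decides or if all four must succeed, but the plan says neither. The practical risk does not depend on the exact percentage: the outcome the trial was sized for can fail and the trial still be called positive.

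**What to change.** **Preferred change, in Outcomes and Data Analysis.**

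1. State that MDD occurrence through the 12-month follow-up is the sole or first-tested primary outcome at two-sided 0.05. This follows the plan's own primary aim and keeps 80% power at 282 per arm.
2. Name one time point and one contrast for each of remission, ISI and PHQ-9.
3. Test those three only if MDD succeeds, under a pre-stated error-controlling rule such as a fixed sequence or Holm. The order is the sponsor's choice.
4. Report other visits as supportive estimates with confidence intervals, and replace the blanket threshold sentence for the primary outcomes.

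**Alternative, if the insomnia aim is to stand alone.** Give each aim 0.025 and one lead outcome: MDD for depression, and ISI or remission for insomnia. Test the aim's other outcome only after its lead succeeds. Pass an aim's 0.025 to the other aim once both its outcomes succeed.

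**Cost.** Wording only, with no extra participants or data. With MDD first, the other three results are not confirmatory when MDD fails: about 20% of the time at HR 0.5 (1 − 0.801), and about 42% and 65% at assumed HRs of 0.6 and 0.7. With the split and recycling, MDD power is about 78% to 80% overall if the insomnia aim succeeds with an assumed 80% to 95% chance. It is about 71% if no alpha is passed on.

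Either change counts as pre-specification only if made before unblinded results are seen. Otherwise, disclose when the rule was set.
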